9.5	Body Weight, Waist Circumference and Body Mass Index (BMI).....	25
9.6	CCI [REDACTED]	26
9.7	Mini-Mental State Examination (MMSE).....	26
9.8	CCI [REDACTED]	26
9.9	Concomitant Medications.....	27
9.10	Extent of Exposure	27
10	Conventions.....	27
10.1	Study Visit Windows.....	27
10.2	Pooling of small centers	28
10.3	Scales: Rules for Scoring and Handling of Missing Data	29
10.3.1	Cohen-Mansfield Agitation Inventory (CMAI).....	29
10.3.2	Clinical Global Impression-Severity of Illness Scale (CGI-S)	29
10.3.3	CCI [REDACTED]	30
10.3.4	CCI [REDACTED]	30
10.3.5	CCI [REDACTED]	30
10.3.6	CCI [REDACTED]	31
10.3.7	CCI [REDACTED]	31
10.3.8	CCI [REDACTED]	32
10.3.9	National Institute of Neurological and Communicative Disorders and Stroke and the Alzheimer's Disease and Related Disorders Association (NINCDS-ADRDA)	33
10.3.10	Hachinski Ischemic Scale (Rosen Modification).....	33
10.3.11	CCI [REDACTED]	[REDACTED]
	[REDACTED]	[REDACTED]

10.3.13	CCI	[REDACTED]
[REDACTED]	[REDACTED]	34
10.3.15	Mini-Mental State Examination (MMSE)	34
11	References.....	36
12	Potential Clinical Relevance Criteria from Protocol.....	37
13	Proposed List of Summary Tables.....	41

1 Introduction

This statistical analysis plan (SAP) documents the statistical methodology and data analysis algorithms and conventions to be applied for statistical analysis and reporting of efficacy and safety data of study 331-12-283. All amendments to the protocol and Addendum to protocol amendment are taken into consideration in developing this SAP.

2 Trial Objectives

Primary: To compare the efficacy of 2 fixed doses (1 mg/day and 2 mg/day) of brexpiprazole with placebo in subjects with agitation associated with dementia of the Alzheimer's type, as assessed by the CMAI after 12 weeks of treatment.

Secondary: To evaluate the safety and tolerability of 2 fixed doses of brexpiprazole (1 mg/day and 2 mg/day) compared with placebo in subjects with agitation associated with dementia of the Alzheimer's type after 12 weeks of treatment.

3 Trial Design

This is a phase 3, 12-week, multicenter, randomized, double-blind, placebo-controlled, 3-arm, fixed-dose trial designed to assess the efficacy, safety, and tolerability of brexpiprazole (1 mg/day and 2 mg/day) in the treatment of subjects with agitation associated with dementia of the Alzheimer's type. The trial population will include male and female subjects between 55 and 90 years of age (inclusive), who are living in either an institutionalized setting or in a non-institutionalized setting where the subject is not living alone. In both the institutionalized and non-institutionalized settings, the subject must have a caregiver who can spend a minimum of 2 hours per day for 4 days per week with the subject in order to assess changes in the subject's condition. All subjects must have a diagnosis of probable Alzheimer's disease according to the National Institute of Neurological and Communicative Disorders and Stroke and the Alzheimer's Disease and Related Disorders Association (NINCDS-ADRDA) criteria.

The trial comprises a 2- to 42-day screening period, a 12-week double-blind treatment period, and a 30-day post-treatment follow-up period. In addition, for all subjects who terminate early from the trial, all attempts will be made to collect mortality data by telephone contact with the subject's caregiver at Week 16.

This trial will be monitored under the supervision of an independent Data Monitoring Committee (DMC). The DMC will monitor safety periodically, based on a predetermined

schedule. The details of the DMC structure and its roles and responsibilities will be documented in a DMC charter.

The trial is organized as follows:

Screening Period

The screening period will range from 2 days to 42 days and will begin when the informed consent form (ICF) is signed, prior to the initiation of any procedures. The screening period may be extended after discussion with and approval by the medical monitor. An interactive voice response system (IVRS) or interactive web response system (IWRS) will be used to obtain the subject study identification number for each subject with a signed ICF.

12-week, Double-blind Treatment Period

Based on a randomization scheme, eligible **CCI** subjects will be allocated in a 1:1:1 ratio at randomization to 1 of the following 3 treatment groups:

- Brexpiprazole 1 mg/day
- Brexpiprazole 2 mg/day
- Placebo

CCI

Subjects will follow a titration schedule, depending upon their assigned treatment group, to gradually increase their dose to their assigned target dose.

Subjects unable to tolerate their assigned dose of brexpiprazole (or matching placebo) will be withdrawn from the trial. Down-titration is not allowed at any time during the study. If a subject is withdrawn, every effort will be made to complete all of the Week 12/Early Termination (ET) evaluations prior to administering any additional medications for the treatment of agitation or other prohibited medications.

Subjects will be evaluated at Baseline, Day 3, and Weeks 2, 4, 6, 8, 10, and 12 during the double-blind treatment period.

All attempts should be made to maintain the subjects' normal routine with regard to physician appointments. Individual circumstances that fall outside this general convention should be discussed with the medical monitor in order to determine appropriateness to

proceed. In addition, the subject's identified caregiver will be contacted by telephone at Weeks 3, 5, and 7 to assess compliance with IMP, confirm any changes to concomitant medications, and assure the subject's well-being. Trial-related efficacy and safety assessments will be performed as outlined in the study protocol.

Follow-up Period

All subjects, whether they complete the trial or are withdrawn prematurely for any reason, will be followed up for a safety evaluation 30 (+ 2) days after the last dose of the IMP during a clinic visit at either the investigator's site or residential facility, if applicable. If a clinic visit is not possible, the subject should be assessed by telephone contact with the subject and a caregiver. For all subjects who terminate early from the trial, all attempts will be made to collect mortality data by telephone contact with the subject's caregiver at Week 16.

Subjects who complete both the 12-week double-blind treatment period and the 30-day safety follow-up visit are eligible to enroll into Trial 331-13-211, which is a 2-month, observational, rollover trial to evaluate the safety of subjects with agitation associated with Alzheimer's disease who previously participated in Trial 331-12-283. For those subjects who plan to enroll into Trial 331-13-211, the 30-day safety follow-up visit for Trial 331-12-283 will occur as a clinic visit at either the investigator's site or residential facility, if applicable.

4 Sample Size and Power Justification

The sample size was calculated based on the treatment effect of 6.5 points with a standard deviation (SD) of 16.5 in the change from baseline (Day 0 visit) to the end of the double-blind treatment period (Week 12 visit) in the CMAI total score, to achieve 85% power at a 2-sided alpha level of 0.05. This results in 117 subjects in each of the groups (i.e., brexpiprazole 1 mg/day, brexpiprazole 2 mg/day, and placebo). After allowance of 10% non-evaluable subjects, the total number of subjects to be randomized is 132 per treatment arm. The sample size was estimated based on a 1:1:1 randomization ratio (brexpiprazole 1 mg/day, brexpiprazole 2 mg/day, placebo).

CCI [REDACTED]

[REDACTED] the total number of subjects to be randomized
will be approximately 420 CCI [REDACTED]

CCI
[REDACTED]

5 Data Sets for Analysis and Missing Data

5.1 Data Sets for analysis

The following analysis samples are defined for this trial:

Randomized Sample: consists of all subjects who were randomized into this trial. Subjects are considered randomized when they are assigned a treatment number by IVRS at the end of Screening Period. A subject receiving trial treatment outside of the IVRS will not be considered randomized, but safety will be reported.

Safety Sample: consists of all subjects who were administered at least one dose of IMP. Subjects will be excluded from this population only if there is documented evidence (ie, drug dispensed = drug returned or no trial drug dispensed) that the subject did not take trial drug. If a subject is dispensed trial medication and is lost to follow up, he/she will be considered exposed.

Efficacy Sample: The intent-to-treat (ITT) population consists of all subjects in the randomized sample, who took at least 1 dose of IMP (excluding subjects randomized to brexpiprazole 0.5 mg/day) and have a baseline and at least one postbaseline evaluation for the CMAI total score.

CCI
[REDACTED]PPD
[REDACTED]PPD
[REDACTED]PPD
[REDACTED]

The core dataset for all efficacy analyses is based on the modified ITT population, which is defined in the efficacy sample above. However, as described below, in order to handle missing data and restrictions imposed by different types of analyses (eg, change from baseline analysis), other datasets derived from the ITT population will be used for the efficacy analyses.

5.2 Handling of Missing Data

The CMAI is utilized as the primary efficacy assessment of a subject's level of agitated behaviors. The CMAI consists of 29 items all rated on a 1 to 7 scale with 1 being the "best" rating and 7 being the "worst" rating. The CMAI Total Score is the sum of ratings for all 29 items. The possible total scores are from 29 to 203. The CMAI Total Score will be unevaluable if less than 24 of the 29 items are recorded. If 24 to 28 of the 29 items are recorded, the total score will be the mean of the recorded items multiplied by 29 and then rounded to the first decimal place.

CCI
[REDACTED]
[REDACTED]
[REDACTED]
[REDACTED]
[REDACTED]
[REDACTED]

The primary efficacy variable is the change from baseline to Week 12 in the CMAI total score.

In general, missing data will be handled by analysis of Mixed effect Model Repeat Measurement (MMRM) methodology based on observed-case (OC) data from protocol-specified visits in the ITT population under the assumption of missing at random (MAR).

The OC dataset consists of actual observations recorded at each visit during the double-blind acute treatment phase, and no missing data will be imputed.

CCI
[REDACTED]
[REDACTED]
[REDACTED]
[REDACTED]
[REDACTED]
[REDACTED]
[REDACTED]
[REDACTED]

6 Study Conduct

6.1 Subject Disposition and Reasons for Discontinuations

Subject disposition is summarized for the randomized sample. Disposition is summarized by treatment group and by subgroup of gender, age (<65; >=65 and <75; or >=75), race, and region (North America or Other).

Reasons for discontinuation will be summarized for the randomized sample by treatment group and by subgroup of gender, age, race, and region.

6.2 Treatment Compliance

Based on the Study Medication panel of the CRF, compliance in taking study medication is calculated by dividing the number of tablets taken by the total number of tablets the subjects were scheduled to take during the study period. For lost-to-follow up subjects, last study medication end date record will be used as the treatment end date.

6.3 Protocol Deviation

Protocol deviations are summarized by center and type of deviation for randomized subjects by treatment group. A listing of protocol deviations will also be generated.

7 Baseline Characteristics

7.1 Baseline Definition

For analyses of the double blind treatment period data, the baseline is the Baseline measurement (expected to be at Day 0). Baseline measurement is defined as the last available measurement prior to the start of double-blind study medication.

7.2 Demographic Characteristics

Baseline demographic characteristics including age, gender, race, ethnicity, height, weight, waist circumference, and body mass index (BMI) will be tabulated by treatment group for all randomized subjects. Additional summaries by the following subgroups will be also generated: by gender, by age group (<65; >=65 and <75; or >=75), by race, and by region (North America or Other).

Mean, range and standard deviation will be used to describe continuous variables such as age. Frequency distributions will be tabulated for categorical variables such as race.

7.3 Disease History

A summary of medical, psychiatric, neurological (excluding Alzheimer's), and Alzheimer's disease history will be presented for the Randomized Sample (by treatment group and overall).

7.4 Baseline Disease Characteristics

For the Randomized Sample, baseline and baseline disease characteristics will be summarized by treatment group and overall. The following baseline characteristics will be summarized at baseline: number (%) of institutionalized / non institutionalized subjects; CMAI total score; **CCI**

CGI-S score, NPI total score; NPI-AA item score; MMSE score; CCI

Number of subjects with presence of psychotic symptoms will be summarized at baseline using NPI Delusion and Hallucination score. The counts will be provided for the following categories: NPI item score ≥ 4 , ≥ 5 , ≥ 6 on either hallucination or delusion score.

All patients randomized under original protocol, amendment 1, and amendment 2 is assumed to be institutionalized and will be included in institutionalized subgroup.

8 Efficacy Analysis

All efficacy analyses pertaining to the double blind treatment period will be performed on the Efficacy Sample, and subjects will be included in the treatment group as randomized.

CCI

Statistical comparisons are based on 2-sided, 0.05 significance levels.

NPI endpoints are collected using NPI-NH for institutionalized subjects and NPI/NPI-NH for non-institutionalized subjects. Since each score derivation of the NPI items is based on the frequency and severity scores only, no distinction will be made due to the instrument used. All analysis of NPI based endpoints will be based on totality of data, unless specified otherwise.

8.1 Primary Efficacy Endpoint

The primary efficacy endpoint is the change from the baseline (Day 0 visit) to the end of the double blind treatment period (Week 12 visit) in CMAI Total Score.

8.1.1 Primary Efficacy Analysis

The primary endpoint will be analyzed using a mixed-effect model repeated measure (MMRM) model. The primary efficacy outcome measure is the mean change from baseline (Day 0 visit) to the end of the double-blind treatment period (Week 12 visit) in the CMAI total score. The primary statistical comparisons of interest are brexpiprazole 2 mg/day versus placebo and brexpiprazole 1 mg/day versus placebo. The null hypotheses of these comparisons are that there is no difference between the brexpiprazole treatment groups and placebo in change from baseline to endpoint in CMAI total score. To protect the experiment-wise 2-sided alpha level at 0.05 when making 2 comparisons of brexpiprazole doses versus placebo, the statistical testing will be carried out using a hierarchical testing procedure in the order of 1) comparison of 2 mg/day brexpiprazole versus placebo and 2) comparison of 1 mg/day brexpiprazole versus placebo. Thus, if the test yields a statistically significant result at 0.05 (2-sided) for the comparison of 2 mg/day brexpiprazole versus placebo, then the comparison of 1 mg/day brexpiprazole versus placebo will be tested at an alpha level of 0.05 (2-sided).

The primary analysis will be performed on the Efficacy Sample which includes all randomized subjects who took at least one dose of IMP in the double blind treatment period and who have both a baseline and at least one post-randomization CMAI Total Score during the double blind treatment period. The primary efficacy analysis will be performed by fitting a MMRM analysis with an unstructured (UN) variance covariance structure in which the change from the baseline in CMAI Total Score (Week 2, 4, 6, 8, 10, 12) will be the dependent variable based on the OC data set. The model will include fixed class-effect terms for treatment (1 mg/day, 2 mg/day, and placebo), trial center, visit week, and an interaction term of treatment by visit week and include the interaction term of baseline values of CMAI Total Score by visit week as covariates. The primary comparison between a brexpiprazole and the placebo arm at Week 12 will be estimated as the difference between Least Squares (LS) means from the interaction term of treatment by visit week utilizing the computing software SAS procedure PROC MIXED.

[figure not shown]
CCI

[figure not shown]
8.1.2 Technical Computation Details for Primary Efficacy Analysis

8.1.3 Sensitivity Analyses for Primary Efficacy Endpoint

8.1.4 Subgroup Analyses for Primary Efficacy Endpoint

Subgroup analyses of change from baseline in CMAI Total Score to every study week in the double blind treatment period will be performed by the following factors:

- Gender
- Race (White and All Other Races)

- Age group (<65; \geq 65 and <75; or \geq 75)
 - Region (North America and Other)

A horizontal bar chart titled 'CCI' in red at the top left. The y-axis has eight categories labeled 1 through 8. Each category has a black horizontal bar representing its CCI value. Category 1 has the shortest bar, while categories 2, 3, 4, 6, 7, and 8 have very long bars extending off the right edge of the chart area.

Category	CCI Value (approx.)
1	10
2	95
3	98
4	99
5	25
6	95
7	98
8	99

8.2 Key Secondary Analysis

[figure not shown]
The key secondary efficacy variable is the change from baseline to endpoint in the CGI-S score, as related to agitation. It will be analyzed by the same statistical methodology specified for the analysis of the primary efficacy variable, based on the Efficacy Sample. In order to control the overall type I error rate for this key secondary efficacy analysis, a hierarchical testing procedure will be used so that the overall experiment-wise type I error rate is maintained at 0.05. Thus, if the primary efficacy analysis for the CMAI total score yields a statistically significant result at 0.05 (2-sided) for both of the comparisons of brexpiprazole 1 mg/day and 2 mg/day versus placebo, then the corresponding comparison for this key secondary efficacy variable (CGI-S score) will be tested at an alpha level of 0.05 (2-sided) using another hierarchical testing procedure in the order of brexpiprazole 2 mg/day versus placebo and brexpiprazole 1 mg/day versus placebo. Thus, brexpiprazole 1 mg/day versus placebo will be tested only if brexpiprazole 2 mg/day versus placebo reaches significance at 0.05 (2-sided) for this key secondary efficacy variable.

A horizontal bar chart titled '8.3' in the top-left corner. The y-axis labels are 'CCI', '███████████', '███████████', '███████████', '███████████', '███████████', and '███████████'. The bars represent CCI values, with the first bar being red and the others black. The last bar has a white rectangular cutout at its right end.

- CCI
-
-
-
-
-

Summary statistics will be provided by treatment groups. Statistical comparisons will be evaluated using the same MMRM model described in the primary analysis at a nominal 0.05 level (two-sided).

8.6

CCI

- A series of five horizontal black bars of varying lengths, decreasing from left to right. The first bar is the longest, followed by a shorter one, then a medium-length one, another short one, and finally the shortest bar on the far right.

8.7 Actigraphy and eDiary Data

Since actigraphy and eDiary are tools to assist the CST in monitoring CMAI rater training, actigraphy and eDiary information will not be made available to site personnel, will not be included in the clinical database, and will not be statistically analyzed.

9 Safety Analysis

Standard safety variables to be analyzed include AEs, clinical laboratory tests, vital signs, ECGs, body weight, waist circumference and physical examination. In addition, data from the following safety scales will be evaluated: MMSE score, CCI [REDACTED]
[REDACTED]
[REDACTED]

[REDACTED] Prospectively defined criteria will be used to identify potentially clinically relevant abnormal values for clinical laboratory tests, vital signs, ECGs, and body weight.

Safety analysis will be conducted based on the Safety Sample. In general, baseline of a safety variable is defined as the last observation of the variable before taking the first dose of IMP, unless specified otherwise.

9.1 Adverse Events

All adverse events will be coded by primary system organ class (SOC) and Medical Dictionary for Regulatory Activities (MedDRA version 19.0) preferred term (PT). AEs that are gender-specific, e.g., ovarian cancer, will have their incidence rates evaluated for the specific gender. The incidence of the following events will be summarized by treatment group:

- a) Treatment-emergent AEs (TEAE) by SOC and PT
- b) TEAEs at least 5% in the brexpiprazole group and twice greater than placebo
- c) TEAEs at least 2% in the brexpiprazole group and greater than placebo
- d) TEAEs by severity
- e) Potentially drug-related TEAEs
- f) TEAEs with an outcome of death
- g) Serious TEAEs
- h) TEAEs leading to discontinuations
- i) EPS-related AEs
- j) EPS-related AEs by time

- k) AEs of special interest
- l) TEAEs by gender, race, age and region

EPS-related AEs will be grouped into five categories.

- 1) Dystonic Events, which include cervical spasm, dystonia, emprosthotonus, muscle contractions involuntary, muscle rigidity, muscle spasms, muscle spasticity, myotonia, nuchal rigidity, oculogyration, opisthotonus, pleurothotonus, risus sardonicus, torticollis, and trismus;
- 2) Parkinsonian Events, which include akinesia, asterixis, athetosis, bradykinesia, cogwheel rigidity, essential tremor, extrapyramidal disorder, freezing phenomenon, gait festinating, hypertonia, hypokinesia, hypokinesia neonatal, intention tremor, masked facies, parkinson's disease, parkinsonian crisis, parkinsonian gait, parkinsonian rest tremor, parkinsonism, tremor, and tremor neonatal;
- 3) Akathisia Events, which include akathisia, hyperkinesia, and psychomotor hyperactivity;
- 4) Dyskinetic Events, which include ballismus, buccoglossal syndrome, choreoathetosis, clumsiness, dyskinesia, dyskinesia neonatal, dyskinesia oesophageal, fumbling, nodding of head, on and off phenomenon, and tardive dyskinesia;
- 5) Residual Events, which include chorea, huntington's chorea, muscle twitching, and myoclonus.

cci

The following AEs of special interest will be summarized by PT terms only:

- 1) Fall
- 2) Orthostatic hypotension
- 3) Syncope
- 4) Dizziness

Treatment-emergent AEs are defined as AEs with an onset date on or after the start of double-blind treatment. In more detail, TEAEs are all adverse events which started after start of double blind study drug treatment; or if the event was continuous from baseline and was worsening, serious, study drug related, or resulted in death, discontinuation, interruption or reduction of study therapy. Adverse Events occurring up to 30 days after the last day of double-blind dosing will be included in the summary tables.

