9.10 Extent of Exposure

The start date of double-blind study therapy - brexpiprazole or placebo - will be the first day of double-blind dosing. The number and percentage of subjects, who receive double-blind study medication, will be presented by week and by treatment group. Each dosing week will be based on the actual week; i.e., Day 1-7 in Week 1, Day 8-14 in Week 2, etc. This summary will be performed on the Safety Sample.

The number and percentage of completers will be presented by week and by treatment group.

The mean daily dosage will be summarized by week and treatment group using descriptive statistics. The mean daily dosage per subject per week will be determined for each week of the study. This will be calculated by dividing the sum of individual total doses by the number of days in the week interval. The summary will contain for each treatment group the number of subjects receiving double-blind study medication, and the mean and range of the mean daily dose for each week.

10 Conventions

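### The SAP gives two treatment-emergent AE rules that do not match, and the fuller one, read literally, counts a continuing pre-dose event that was already serious and has not changed

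*SAP*

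**What the plan says.** Section 9.1 contains three sentences on the point.

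- The first is a complete definition by onset: "Treatment-emergent AEs are defined as AEs with an onset date on or after the start of double-blind treatment".
- The second is introduced as giving more detail. It begins "TEAEs are all adverse events which started after start of double blind study drug treatment; or if the event was continuous from baseline". The second route that it opens in this way is for an event that was "continuous from baseline and was worsening, serious, study drug related, or resulted in death, discontinuation, interruption or reduction of study therapy".
- The third sets the end of the window: "Adverse Events occurring up to 30 days after the last day of double-blind dosing will be included in the summary tables".

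Section 9.10 defines the start of double-blind therapy by day, not clock time: it "will be the first day of double-blind dosing". Section 10.1 calls that day Day 1.

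The TEAE label governs items a to h and l of the table list in section 9.1. These run from "Treatment-emergent AEs (TEAE) by SOC and PT" through the 5% and 2% incidence tables, severity, relatedness, deaths, serious events and discontinuations to the subgroup tables. Items i to k (EPS-related events and events of special interest) are labelled as AEs, not TEAEs.

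**The concern.** A sentence that elaborates a definition should narrow it or make it operational. This one changes the definition in two ways. It moves the boundary from *on or after* to *after*, and it admits events that began before treatment, which the first sentence excludes. No sentence says which rule governs.

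Counting pre-existing events that worsen on treatment is not the fault. The fault is that the first sentence leaves them out, and that seriousness stands in the second as a sufficient condition with no requirement that anything happened after first dose.

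Safety and tolerability is the trial's secondary objective (section 2). A literal derivation would place some events in the serious TEAE table that did not emerge on treatment, and might omit some that began on the day of first dose.

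**Working it through.** The SAP has no figure to reproduce here. The check sets the two sentences side by side as classification rules.

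- Rule A (first sentence): onset date ≥ date of first dose.
- Rule B (second sentence, literal): onset after start of treatment; **or** continuing from baseline **and** at least one of: worsening, serious, drug related, or a listed outcome (death, or stopping, interrupting or reducing therapy).

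| Event | Rule A | Rule B |
|---|---|---|
| 1. Onset after the first-dose day | yes | yes |
| 2. Onset on the first-dose day | yes | no by date; by time, depends on the order of dose and onset |
| 3. Pre-dose onset, continuing, worsened | no | yes |
| 4. Pre-dose onset, continuing, serious, unchanged | no | yes |
| 5. Pre-dose onset, continuing, drug related or with a listed outcome | no | yes |
| 6. Pre-dose onset, continuing, no listed condition | no | no |

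The rules always disagree in classes 3, 4 and 5, and can disagree in class 2.

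Three ways of reading the two sentences together:

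1. **Rule B governs.** Classes 3 and 5 are counted, as is usual. Class 4 is counted, which is the problem. Class 2 is at risk on a strict date comparison.
2. **Either rule suffices (union).** Class 2 is kept and classes 3 and 5 are counted. Class 4 is still counted.
3. **Rule A governs.** Class 4 is excluded, but so are classes 3 and 5.

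No reading both counts worsened baseline events and keeps out class 4.

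**Scale of one subject.** Section 4 plans 132 randomized per arm. The Safety Sample, on which safety is analysed, may differ. Section 9.1 refers to the brexpiprazole group in the singular although there are two doses, so both denominators are shown.

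- Per dose: 1/132 = 0.76 percentage points. 0.02 × 132 = 2.64, so 2% is reached at 3 subjects. 0.05 × 132 = 6.6, so 5% is reached at 7.
- Doses pooled (assumption): n = 2 × 132 = 264 and 1/264 = 0.38 points. 0.02 × 264 = 5.28, so 6 subjects. 0.05 × 264 = 13.2, so 14.

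These figures show only how coarse the thresholds are. The SAP gives no frequency for classes 2 to 5, so the number of reclassified subjects cannot be computed.

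**The case against.** The strongest reply is that the second sentence announces itself as the fuller version and so takes precedence. That largely stands. A reader might infer that the tables hang on which sentence a programmer happens to pick, and that worsened baseline conditions could be lost. That would require ignoring the second sentence altogether, which the text does not invite.

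On first-dose-day events, *after start of treatment* ordinarily means once treatment has begun, and the only sentence that speaks of an onset date includes the day itself. Losing these events takes a strict date inequality that overrides the one explicit date rule. So this is a possible consequence of the wording, not a certain one.

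A reader might also infer that screening-period events in general are attributed to the drug. The text does not support this. Only events still present at baseline can qualify, treatment-emergent is a label about timing, and relatedness has its own table (item e). An event that was serious before dosing and stayed unchanged cannot result from the assigned arm, so under randomization it is expected to add noise and not to favour an arm.

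Finally, a reader might take the one-subject arithmetic to mean that single reclassified events will move terms into or out of the 2% and 5% tables. Those tables also require a comparison with placebo (for the lower threshold, "TEAEs at least 2% in the brexpiprazole group and greater than placebo"), so reaching the percentage is not enough by itself.

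What survives all of this is class 4. Neither precedence for the second sentence nor a union of the two removes it. The drafters may have meant *became serious*, but the text does not say so.

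**Conclusion.** The point holds as a fault in a stated rule, not as a missing detail. The two sentences define different sets of events. The one that is probably operative counts a continuing, already serious, unchanged pre-dose event as a serious TEAE, and on date-level data it can exclude first-dose-day events that the other includes.

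The effect is confined to items a to h and l of the safety tables in section 9.1. Efficacy analyses and type I error control are untouched. The size cannot be derived from the SAP and is probably small. For class 4, randomization means no arm is expected to be favoured. Class 2 events follow dosing, so randomization gives no such assurance for them, but they are lost only on the strict date reading and nothing in the SAP points to an imbalance.

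This rests on reading the listed conditions as alternatives, as the sentence's *or* indicates, and on derivation at date level, as section 9.10 suggests. It should be corrected because the safety tables serve the secondary objective and the correction is cheap.

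**What to change.** Replace the definition sentences and the window sentence with one programmable rule, for example:

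> A TEAE is an AE whose onset date is on or after the date of first double-blind dose, or an AE continuing from before first dose that, after first dose, worsened, became serious, was assessed as related to study drug, or led to death or to study therapy being discontinued, interrupted or reduced. Onset or change is counted up to 30 days after the last dose.

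This settles Day 1, requires a post-dose change, assessment or outcome for pre-existing events, and says what the 30-day limit applies to. Relatedness is worded as an assessment because it is a judgement about an event, not a state the event enters. No clock-time test is added, since the SAP does not mention one.

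Dose reduction stays in the list because the SAP names it. Section 3, however, says down-titration is not allowed at any time, so the two passages must be reconciled.

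The cost is one paragraph of SAP text and one derivation in the AE dataset. Compared with the literal second sentence, slightly fewer events would count as serious TEAEs. Events on the day of first dose would all count, including any that began earlier that day than the dose.
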